5. RECRUITMENT

5.1 Site Eligibility

Potential sites will be identified by Spectrum Therapeutics regional medical teams (ST MSL), based on feasibility criteria. Sites expressing interest in study participation will undergo an extensive feasibility evaluation. All sites will be required to satisfy the following eligibility criteria:

1. Site physician profile (pain specialist, rheumatologist, neurologist, general practitioner);
2. Site must recruit a minimum of five new chronic non-cancer pain subjects per month, or large chronic non-cancer pain database willing to start subjects on Spectrum Therapeutics products;
3. Previous experience with observational or clinical studies (has been a site, or enrolled subjects in a registry);
4. Access to, willing to participate in, an ethics review;
5. Minimum structure (required SOPs, internet access, *REDCap cloud* support) and human resources (study site personnel);
6. Interest in participating in Real World Data collection;
7. Experience with authorizing/prescribing medical cannabis.

To ensure a consistent approach to the subjects and the study, all participating site physicians will be required to complete ICH GCP training (unless already in possession of ICH GCP certificate).

Suggested resource: <https://about.citiprogram.org/en/series/good-clinical-practice-gcp/>

Sites who risk ineligibility for insufficient enrollment or compliance will be contacted by the Sponsor for possible remedial action.

5.2 Investigator Training

After completing the feasibility evaluation, and upon attaining site-specific ethics approval, and ICH GCP certificate, site physicians and any study site personnel, will attend a live Investigator training webinar, or follow a recording of a live webinar. A certificate of attendance will be issued upon (1) completion of the training modules and (2) successful passing of a training-focused quiz. Investigator training will be available in the native language of the site physician. Completion of the training is required prior to enrolling subjects. The investigator training objectives will include the following.

1. Overview of medical cannabis in chronic pain.
2. Overview on Real World Evidence and research methods.
3. Overview of the registry Protocol, and other study documents.
4. Spectrum Therapeutics Safety training (common AEs, contraindications, and information about local regulatory reporting requirements).
5. Overview of the Investigator Communication Platform.
6. Overview of *REDCap Cloud* data management system.

On-site support from the ST MSL team will be continuously available to sites throughout the study.

6. SUBJECT SELECTION AND WITHDRAWAL CRITERIA

6.1 Subject Inclusion Criteria

Subject eligibility will be assessed after subjects have signed and dated the eICF. Subjects must meet all of the following criteria to be eligible for enrollment into the study:

1. Subject is ≥ 25 years of age with a diagnosis of chronic non-cancer pain defined as pain lasting or recurring over a period > 3 months (IASP-ICD-11 classification²⁷, refer to Appendix 6).
2. Subject is, in the physician's opinion, a candidate for medical cannabis. Candidate status will be determined based on local regulation, common clinical practice, available guidelines and scientific literature, and the physician's expertise or experience with medical cannabis products.
3. Subject received a prescription/authorization for a product in the medical channel of Spectrum Therapeutics.
4. Subject is able to read and understand the informed consent form and complete the study questionnaires.

6.2 Subject Exclusion Criteria

Subjects meeting any of the following criteria will not be eligible for participation in the study:

1. Subject refuses to provide informed consent or participate in any aspect of the study.
2. Subject is pregnant or lactating.
3. Subject has a history of psychosis or schizophrenia (or other significant psychiatric disorder), including among first-degree relatives.
4. Subject has a suspected or confirmed cardiovascular disease.
5. Subject is a liver transplant recipient or with severely compromised liver function.

6.3 Subject Withdrawal from Study Participation

Subjects are free to withdraw from the study at any time. Subjects who start taking medical cannabis from another licensed producer or withdraw consent for study participation will be contacted by the site physician or study site personal to complete an Exit assessment as soon as possible.

Subjects that have received ST products and started using them for treatment of chronic pain, will be entered in the data analysis population, unless they have withdrawn consent together with withdrawing from the study. This is described in more detail, in the Statistical Analysis Plan.

The site physician, by joining the study, confirms commitment to subject retention through coaching, counseling, and education.

The site physician may withdraw a subject from the study in the following circumstances:

- Subject experiences a serious adverse event (SAE) or other safety concerns.
- Subject does not benefit from ST product treatment.
- Subject meets any exclusion criteria.
- Noncompliance with the study protocol.
- Administrative reasons or study termination (e.g., Sponsor decision).
- Other factors determined by the physician to affect the eligibility of subjects to continue.

A record of the reason for withdrawal will be maintained for reporting and publication. Subjects who are withdrawn or removed from the study will be replaced if the study is still in enrollment.

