In the event of ST treatment discontinuation, or study dropout, physicians will be asked to follow-up with subjects to complete the ST Discontinuation Assessment and Exit assessment (Appendix 4). Based on physician answers to ST Discontinuation Assessment, subjects will either stay enrolled in the study (e.g., discontinue all cannabis treatment, but continue to be monitored by site physician for chronic pain), or be withdrawn (e.g., unwilling to stay in the study, switched cannabis licensed producer).

A complete schedule of events is provided in **Table 1**.

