7.2.7.2 SAE Definition

An AE will be considered serious if it results in 1 or more of the following outcomes:

- Death
- Life-threatening (i.e., at immediate risk of death)
- Subject in-subject hospitalization or prolongation of existing hospitalization
- Persistent or significant disability/incapacity
- Congenital anomaly/birth defect
- Any other AE that the Investigator or company judges to be serious or which is defined as serious by the local regulatory agency.

Important AEs that may not result in death, be life threatening, or that do not require hospitalization may be considered serious when, based upon appropriate medical judgment, they may jeopardize the subject or may necessitate medical or surgical intervention to prevent one of the outcomes listed in the definition above. For this registry, the Important Medical Event (IME) list will be used as a reference for the assessment of medically significant adverse events³⁰.

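### Section 6.3 lets an SAE, a safety concern or an exclusion criterion newly met on treatment end registry follow-up, with no safety follow-up defined afterwards

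*Protocol*

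**What the plan says.** Protocol section 6.3 introduces its list with "The site physician may withdraw a subject from the study in the following circumstances". Two entries matter here: "Subject experiences a serious adverse event (SAE) or other safety concerns" and "Subject meets any exclusion criteria". Both concern leaving the study, not only stopping ST products.

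The exclusion criteria in section 6.2 include "Subject is pregnant or lactating", "Subject has a history of psychosis or schizophrenia (or other significant psychiatric disorder), including among first-degree relatives" and "Subject has a suspected or confirmed cardiovascular disease", as well as severely compromised liver function. Section 6.3 does not say whether a criterion must have been present at enrollment.

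Section 6.3 also keeps treated subjects in the analysis population unless they withdraw consent as well, requires the reason for withdrawal to be recorded, and replaces withdrawn subjects while enrollment is open. Section 9.3 retains data collected before withdrawal. Section 3.1 sends SAEs to the sponsor's pharmacovigilance department in real time.

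Section 3.1 describes another route after ST is stopped. A subject may stay enrolled, the example being to "discontinue all cannabis treatment, but continue to be monitored by site physician for chronic pain". Its examples of withdrawal are unwillingness to stay and a change of licensed producer. Appendix 4 lists an adverse event among the reasons for stopping ST, and has a branch in which the subject remains in the registry and completes the planned follow-ups.

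**The concern.** Section 4.1 states that the protocol assigns no intervention and that the investigator does not control prescribing. Taking a subject out of the registry therefore changes no exposure under the protocol; it only stops data collection.

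Assessing safety and tolerability is a stated objective (section 2.1.3), and adverse-event incidence by product and formulation is the safety endpoint (section 7.1). Section 3.1 justifies the later time-points partly by long-term screening for adverse events. A rule under which a serious event, or a new psychiatric, cardiovascular, hepatic or pregnancy finding, can itself end observation works against that purpose.

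The resulting loss is informative: follow-up stops because of the outcome being studied. It is also left to individual physicians at an estimated 50 to 150 sites, so it may differ between sites.

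**Working it through.** **No planned figure to reproduce.** The target of 1500 is two milestones (750 + 750) with no calculation behind it, and it does not bear on this point. The check is a reading of the passages plus a count from the visit schedule.

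**1. Follow-up lost by one withdrawn subject.** Inputs: 12 months of follow-up (section 3.1) and scheduled follow-ups at months 1, 2, 3, 4, 6, 8, 10 and 12 (Table 1), 8 in all. The physician follow-ups are those at months 2, 4, 8 and 12. For withdrawal at month t, with the visit at t completed, months lost = 12 − t and follow-ups lost = the scheduled months after t.

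| Withdrawn at month | Months lost | Follow-ups lost | Of which physician follow-ups |
|---|---|---|---|
| 2 | 12 − 2 = 10 of 12 | 6 of 8 (3, 4, 6, 8, 10, 12) | 3 of 4 (4, 8, 12) |
| 4 | 12 − 4 = 8 of 12 | 4 of 8 (6, 8, 10, 12) | 2 of 4 (8, 12) |
| 8 | 12 − 8 = 4 of 12 | 2 of 8 (10, 12) | 1 of 4 (12) |

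The same arithmetic holds for withdrawal for any reason. What is particular here is that the event decides who is withdrawn and when.

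**2. What is kept and what is lost.**

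- Kept: the triggering event once recorded, everything before it, the subject's place in the analysis population, and the reason for withdrawal.
- Lost: the later course of the event. The Physician AE form in Appendix 2 asks for end date, outcome (including still-open categories), and whether the reaction disappeared on stopping and reappeared on restarting. Some causality criteria in section 7.2.7.4 also rest on re-exposure. Table 1 schedules this form at physician and unscheduled visits, and none is defined after withdrawal.
- Lost: any later or recurrent event and the remaining person-time.
- Not recovered elsewhere: the Exit form in Appendix 5 is one confirmation checkbox. Section 8.3 promises efforts to contact subjects who leave early but gives no safety content or duration.

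**3. Effect on the endpoint.** If incidence counts subjects with a given event, the triggering event is already counted and only a different, later event can be missed. If events are counted, recurrences after t are missed too. A rate per person-time corrects for shorter observation only if withdrawn subjects would have had the same later risk as those who stay, which is doubtful when an event selected them. Replacement restores the head count but not the lost period after the event.

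**4. Side by side.** A subject who stops ST after an SAE may stay enrolled under section 3.1 and Appendix 4, or may be withdrawn under section 6.3. No rule says which applies. Appendix 4 contains both a stay-enrolled and a no-longer-eligible branch, but its printed text does not show which reasons lead to which.

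**5. Pregnancy as an example.** "Congenital anomaly/birth defect" is a seriousness criterion in section 7.2.7.2. A subject withdrawn on becoming pregnant during the year is no longer under scheduled observation, and no other means of learning the outcome is described.

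**The case against.** The strongest reply is that the data are better protected than section 6.3 suggests when read alone. Withdrawal is permitted, not required, and the same section commits physicians to retention. Sections 6.3 and 9.3 keep the subject and the earlier data, and SAEs reach pharmacovigilance without waiting for a visit. All of this stands. A reader might infer that affected subjects leave the safety dataset, or that the SAE that prompted withdrawal goes uncounted. The documents contradict both inferences.

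The exclusion-criterion entry also has a legitimate use: removing subjects found after enrollment to have been ineligible. Several criteria describe history or prior status and fit that use. This stands as well, and is a reason to limit the entry and not delete it.

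A reader might add that a pregnancy conceived late in the year would end after the last visit in any case. That follows from the one-year follow-up and not from section 6.3, so it is no part of this point.

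Finally, the pharmacovigilance department might pursue outcomes on its own. The protocol does not say so, and does not say that such information would return to the registry database. None of the safeguards defines follow-up after withdrawal, and an analysis plan cannot recover data that were never collected.

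**Conclusion.** The point holds for the period after the event. Section 6.3 allows observation to end because of a safety event, without defined safety follow-up, and this is inconsistent with the stay-enrolled route in section 3.1 and Appendix 4.

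The consequence is informative loss of event outcomes, later or recurrent adverse events, and person-time. It can understate later and recurrent events by product. It does not show that overall adverse-event incidence, or the count of first SAEs, is understated.

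For one subject the loss runs from 10 of 12 months (withdrawn at month 2) to 4 of 12 (month 8). The total across the registry cannot be estimated, because the protocol gives neither an expected SAE frequency nor any indication of how often physicians would use the rule. The conclusion assumes that the exclusion-criterion entry applies to criteria arising during follow-up, which the wording permits but does not state. The primary objective, a description of prescribing patterns, limits the weight of the point, but the correction is cheap and worth making.

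**What to change.** In section 6.3:

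- Remove an SAE or safety concern as a ground for leaving the registry.
- Limit the exclusion-criterion entry to subjects found to have been ineligible at enrollment.
- State that any change in ST remains the physician's decision, that stopping is recorded on the ST Discontinuation form, and that scheduled follow-up then continues to month 12 unless the subject withdraws consent or leaves for another reason listed in the protocol.

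Reconcile section 3.1 and Appendix 4 with this text, so that stopping ST because of an adverse event leads to the stay-enrolled branch.

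The cost is protocol wording and the completion of visits already scheduled for these subjects. No new assessment or follow-up beyond month 12 is needed, and treatment decisions are untouched.

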7. OUTCOME ASSESSMENTS

7.1 Study Endpoints

Primary endpoints

- Physician selection of Spectrum Therapeutics (ST) medical cannabis treatment regimen and changes over time in:
 - (1) average daily dose of THC and CBD (in mg);
 - (2) route of administration (inhaled or ingested).

Secondary endpoints

- Subject selection of ST treatment regimen and changes over time in:
 - (1) average daily dose of THC and CBD (in mg);
 - (2) route of administration (inhaled or ingested).
- Change in BPI-SF responses from baseline.
- Change in EQ5D-5L responses from baseline.
- PGI-C for the target treatment goal.
- CGI-I for the target treatment goal.
- In subjects taking an opioid, changes in opioid use over time (calculated as milligram morphine equivalents [MME]/day).
- Among subjects taking other medication, total daily dose change over time.

Safety endpoint

- Incidence of AEs stratified by product and formulation.

7.2 Study Assessments

7.2.1 EQ5D-5L- Euro QoL

EQ5D-5L is a 5-category questionnaire (with a total of 6 questions) assessing mobility, self-care, usual activities, pain/discomfort, anxiety/depression, and overall health on a scale from 0-100 (where 100 denotes the best, and 0 the worst health)²⁸.

7.2.2 BPI-SF

The BPI-SF is a 9-item self-report questionnaire that is quickly and easily administered to subjects with chronic pain. The questionnaire includes 6 pain items that assess the spatial and temporal characteristics of pain (e.g., location, 24-hour worst pain, 24-hour average pain, pain right now); 2 items that ask about current treatments assumed for chronic pain and pain relief; and 1 pain interference item (with parts A–G) where respondents rate the level of interference of pain with general activity, mood, walking ability, normal work, social relations, sleep, and enjoyment of life over the past 24 hours²⁴.

7.2.3 PGI-C

The PGI-C is a simple 1-item self-report outcome measure that assesses a subject's overall treatment satisfaction using a 7-point Likert-type scale. The PGI-C shows good performance and high responsiveness in subjects with chronic pain and is often more responsive than primary measures of pain intensity, possibly because the PGI-C captures additional elements of the analgesic response such as physical and psychological functioning²⁵.

7.2.4 CGI-I

The CGI-I is a simple 1-item clinician-reported outcome measure, similar to the PGI-C, that assesses a clinician's overall impression of subject improvement in response to treatment using a 7-point Likert-type scale. Although frequently used in clinical trials focused on mental disorders, the CGI has also been evaluated in a context of chronic pain and correlates well with subject responses to the PGI-C²⁶.

7.2.5 Determination of Opioid Consumption

Physicians will confirm subjects who take an opioid at baseline or who start an opioid during the study, and will be asked to report the opioid type and MME, so that opioid consumption (and any opioid-sparing effect of the ST treatment regimen) can be examined over time.

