9. STATISTICAL METHODS

9.1 Statistical overview

The Sponsor will perform statistical analyses. The Sponsor or designee will extract and analyze descriptive data every 6 months. This will be done to keep sites apprised of study progress. A de-identified summary report will be generated and delivered to all registered site physicians.

The report will indicate:

- The number of physician-collaborators stratified by country.
- The number of subjects enrolled stratified by country.
- Subject demographics, chronic pain classification, and treatment goal.
- Subject concomitant medication use.
- Subject ST treatment regimens.
- Incidence of AEs per individual ST product.

Upon database lock a series of analysis will be conducted to address study objectives. For each analysis, the normality of the data distributions will be ascertained using the Shapiro-Wilk test of normality and Levene's test of equality of error variance. Descriptive statistics (frequencies, means, and standard deviations for normally distributed parametric data; medians and interquartile ranges for nonparametric data) will be used to characterize the sample. Outcome analyses will include a change in ST regimen; a change in reported opioid consumption in MME/day; change in daily dose of other medications, including analgesics, sedatives, and benzodiazepines; change in responses to BPI-SF items and EQ-5DL items; initial PGI-C and changes over time; and initial CGI-I and changes over time. For the safety endpoint, AEs will be tabulated descriptively. Detailed analyses are outlined in the Statistical Analysis Plan.

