Benzodiazepines Dosing Information

Name of drug _____

Daily dose of [baseline_visit][benzo1_name](total mg per day) _____

Check to add additional benzodiazepine medications

Name of drug _____

Daily dose of [baseline_visit][benzo2_name] (total mg per day) _____

Check to add additional benzodiazepine medications

Name of drug _____

Daily dose of [baseline_visit][benzo3_name] (total mg per day) _____

Opioid Dosing Information

Please enter MME (total daily morphine equivalent dose in mg) _____

Other Medication Information

Please indicate name of other drugs not included in the above classes _____

Daily dose (total mg per day), if available _____

ST Regimen Canada

[figure not shown]

Please enter in the table below total daily amount of Spectrum Therapeutics products consumed. Please be conscious of the units provided:

Inhaled cannabis = total number of inhalations per day

Ingested oils = total mL per day

Spray format = total number of sprays per day

Capsules & edibles = total number of capsules or total number of chocolate bar squares per day

	Inhaled Formats (dried flower, extract vaporizers) -- report daily total number of inhalations	Ingested Oil Formats - report daily total number of mLs	Spray Formats - report daily total number of sprays	Low Potency Capsule & Edible Formats - report daily total number of low-potency capsules (i.e. 2.5 mg), number of chocolate bar squares, etc.	High Potency Capsule Formats - report daily total number of high-potency capsules
Red (examples include Spectrum #1-4; Tweed Bakerstreet, Highlands, Houdstooth, Donegal; LBS Sunset)	 inhalations  	 mL  	 sprays  	 capsules  	 capsules  
Orange	 inhalations  		 sprays  		
Purple (examples include LBS Ocean View)	 inhalations  		 sprays  		
Blue (examples include Tweed Penelope)	 inhalations  	 mL  	 sprays  	 capsules  	 capsules  
Green (examples include Tweed Argyle)	 inhalations  	 mL  	 sprays  	 capsules  	 capsules  

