What is their current daily dose of [baseline_visit]
[musrel1_name] (total mg per day)?

At last visit, you indicated that your patient was taking
[baseline_visit][musrel2_name]. Is your patient still taking this
medication?

- Yes
- No

Please select the reason why your patient stopped taking this
medication.

- Side effects
- Cost
- Lack of benefit
- No longer needs/ replaced by medical
cannabis
- Unknown

What is their current daily dose of [baseline_visit]
[musrel2_name] (total mg per day)?

At last visit, you indicated that your patient was taking
[baseline_visit][musrel3_name]. Is your patient still taking this
medication?

- Yes
- No

Please select the reason why your patient stopped taking this
medication.

- Side effects
- Cost
- Lack of benefit
- No longer needs/ replaced by medical
cannabis
- Unknown

What is their current daily dose of [baseline_visit]
[musrel3_name] (total mg per day)?

Existing Benzodiazepines Dosing Information

At last visit, you indicated that your patient was taking
[baseline_visit][benzo1_name]. Is your patient still taking this
medication?

- Yes
- No

Please select the reason why your patient stopped taking this medication.

- Side effects
- Cost
- Lack of benefit
- No longer needs/ replaced by medical cannabis
- Unknown

What is their current daily dose of [baseline_visit] [benzo1_name] (total mg per day)?

At last visit, you indicated that your patient was taking [baseline_visit][benzo2_name]. Is your patient still taking this medication?

- Yes
- No

Please select the reason why your patient stopped taking this medication.

- Side effects
- Cost
- Lack of benefit
- No longer needs/ replaced by medical cannabis
- Unknown

What is their current daily dose of [baseline_visit] [benzo2_name] (total mg per day)?

At last visit, you indicated that your patient was taking [baseline_visit][benzo3_name]. Is your patient still taking this medication?

- Yes
- No

Please select the reason why your patient stopped taking this medication.

- Side effects
- Cost
- Lack of benefit
- No longer needs/ replaced by medical cannabis
- Unknown

What is their current daily dose of [baseline_visit] [benzo3_name] (total mg per day)?

Existing Opioid Dosing Information

At last visit, you indicated that your patient had an MME of [baseline_visit][opioid_mme]. Is your patient still taking opioids?

- Yes
- No

Please select the reason why your patient stopped taking this medication.

- Side effects
- Cost
- Lack of benefit

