- No longer needs/ replaced by medical cannabis
- Unknown

What is their current MME?

Existing Other Medications Dosing Information

At last visit, you indicated that your patient was taking other medications, including [baseline_visit][othmed_name]. Is your patient still taking any of these other prescription medications?

- Yes
- No

Please describe any **changes** to their other existing prescription medications since last visit (including changes to total daily dose)

Concomitant Medications - New

Since last visit, has your patient **started** taking any of the following classes of prescription medication (select all that apply)

- Nonsteroidal Anti-inflammatory Drugs (NSAIDs) and Acetaminophen
- Antidepressants (TCA, SNRI, SSRI)
- Anticonvulsants (gabapentin, pregabalin)
- Muscle Relaxants
- Benzodiazepines
- Opioids
- Other
- Medical Cannabis from a Licensed Producer other than Spectrum

Name of new NSAID/Acetaminophen medication (started since last visit)

Daily dose of [physician_1st_follow][nsaid4_name] (total mg per day)

Name of new antidepressant medication (started since last visit)

Daily dose of [physician_1st_follow][antidep4_name] (total mg per day)

Name of new anticonvulsant medication (started since last visit)

Daily dose of [physician_1st_follow][anticon4_name] (total mg per day)

Name of new muscle relaxant medication (started since last visit)

Daily dose of [physician_1st_follow][musrel4_name] (total mg per day)

Name of new benzodiazepine medication (started since last visit)

Daily dose of [physician_1st_follow][benzo4_name] (total mg per day)

Please enter MME (total daily morphine equivalent dose in mg)

Name of new prescription medication (started since last visit, not covered in above classes)

Daily dose of [physician_1st_follow][othmed4_name] (total mg per day)

Physician AE form

Product information

Do you have any adverse events to report related to this patient?

- Yes
- No

Suspect product(s) name

Start date

_____ (YYYY-MM-DD)

End date

_____ (YYYY-MM-DD)

Route of administration

- oral - oil
- oral - softgel
- oral - spray
- oral - beverage
- oral - chocolate
- oral
- inhalation - smoked
- inhalation - vaporized
- inhalation

Dose (please include amount and unit i.e. mg, ml, #softgels, #inhalations, etc.)

Did reaction disappear after reducing the dose or stopping the product ?

- No
- Yes
- Unknown

Did reaction reappear after same product/treatment was restarted?

- No
- Yes
- Unknown

AE description

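### Section 7.2.5 promises opioid type and MME, but the forms store only a site-converted MME total, so MME/day cannot be recomputed and opioid switches cannot be identified from the database

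*Protocol*

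**What the plan says.** Protocol section 7.2.5 covers subjects on an opioid at baseline and those who start one later. It says physicians "will be asked to report the opioid type and MME", so that consumption and any opioid-sparing effect can be followed over time. Section 7.1 makes this a secondary endpoint: "changes in opioid use over time (calculated as milligram morphine equivalents [MME]/day". Section 9.1 plans the matching analysis: "a change in reported opioid consumption in MME/day".

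The forms ask for less:
- Appendix 1 (baseline) has one opioid field: "Please enter MME (total daily morphine equivalent dose in mg".
- Appendix 2 (follow-up) shows an earlier value, "At last visit, you indicated that your patient had an MME of [baseline_visit][opioid_mme", asks whether the patient still takes opioids, and then asks "What is their current MME".
- For an opioid started since the last visit, Appendix 2 again asks only for a total daily MME.

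Other named classes are recorded by drug. For benzodiazepines, Appendix 1 has a drug name followed by "Daily dose of [baseline_visit][benzo1_name](total mg per day", and Appendix 2 has "Name of new benzodiazepine medication (started since last visit" followed by its daily dose.

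**The concern.** The text and the forms of the same protocol disagree on what is collected. Opioid type is promised and has no field. The number that is collected is already the product of a drug dose and a conversion factor, and neither component is kept. The protocol names no conversion table or calculator and does not say who converts.

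The endpoint is a change within a subject over a year. If the factor applied to a subject changes between visits, through a change of table, a change of staff, or an opioid switch converted inconsistently, the recorded MME moves although intake has not. In the data this looks the same as opioid sparing, or as escalation. An analyst could not separate the two or run a sensitivity analysis without subjects who switched drug.

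**Working it through.** **1. Text against forms.** Section 7.2.5 names two data items, type and MME. Of the three places in Appendices 1 and 2 where an opioid value is entered (baseline, existing opioid at follow-up, new opioid at follow-up), all three take MME and none takes a name, a dose in mg or a route. Follow-up also records whether opioids were stopped and whether an opioid was newly started. A complete stop is therefore visible whatever the factor. A newly started opioid is visible as an event, but not which drug it is or whether it replaced another.

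**2. Comparison with other classes.** NSAIDs/acetaminophen, antidepressants, anticonvulsants, muscle relaxants and benzodiazepines each have drug name and mg per day at baseline, with room for three drugs. At follow-up they have the current dose of each listed drug, and name and dose of a new one. The contrast holds for these five classes.

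**3. What a conversion difference does to the endpoint.** Let D0 and D1 be the true daily opioid amounts at baseline and follow-up, and k0 and k1 the factors applied. Recorded MME is k0 × D0 and k1 × D1.
- Same factor at both visits (k0 = k1 = k): the recorded change is k × (D1 − D0). If D1 = D0 this is zero. A site with an unusual but constant factor rescales a real change in MME and leaves the percentage change untouched.
- Factor lower at follow-up by a ratio r (k1 = k0 / r) and unchanged intake (D1 = D0): the apparent relative fall is 1 − 1/r.

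The protocol gives no factors, so r is an assumption, shown over a range:
- r = 1.25: 1 − 1/1.25 = 0.20, a 20% apparent fall
- r = 1.5: 1 − 1/1.5 = 0.33, a 33% apparent fall
- r = 2.0: 1 − 1/2.0 = 0.50, a 50% apparent fall

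**4. From one subject to the mean.** With equal baseline MME, a share p of opioid users affected, all in the same direction, shifts the mean by p × (1 − 1/r). Assuming p = 10%, that is 0.10 × 0.20 = 2%, 0.10 × 0.33 = 3.3% and 0.10 × 0.50 = 5% of the baseline mean. Errors in both directions partly cancel.

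**5. Reach of the existing checks.** Section 8.2 provides range checks and queries of implausible or inconsistent entries. Section 8.3 provides remote source verification at 10% of sites: 0.10 × 50 = 5 to 0.10 × 150 = 15 sites, leaving about 90% without it. These can catch an implausible total or a transcription error. A plausible MME built with a different factor passes a range check, and outside the verified sites no planned source verification would trace it.

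**The case against.** Entering a converted total is a defensible low-burden choice for an observational registry, and section 9.2 stresses low burden. The endpoint is a within-subject change, so constant differences between sites do no harm to percentage change. The follow-up form displays a previous MME, which gives the person entering data a reference. A common table may be handed out in the training described in section 5.2. Even a central table rests on approximate equivalences, so the proposed change reduces the problem with switches and does not abolish it. All of this stands. It bears on how large the problem is, and does not change the fact that the forms omit an item that section 7.2.5 promises.

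A reader might infer more than the protocol supports:
- **That opioids are the only class without name and dose.** Existing drugs under Other are followed up only by free text, and medical cannabis from another producer is listed with no name or dose field in that part of the form.
- **That MME entries cannot be checked or queried.** Sections 8.2 and 8.3 provide for both. The narrower truth is that MME cannot be recomputed from the database.
- **That sites use non-standard conversions.** The protocol is silent on the table. It is fair to say only that conversion is not specified.
- **That the error outweighs the signal.** Assume a 10–50% conversion error on 50 MME/day, which is 5–25 MME/day, and suppose 20% of users halve their dose. The mean change over all users is 0.20 × 25 = 5 MME/day, which suggests an error 1–5 times the signal. That sets one subject's error against an average diluted by the 80% who do not change. Within a subject who halves, the ratio is 5/25 to 25/25, or 0.2 to 1.0.

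One defence fails. The statistical analysis plan is not at hand, but it could not repair this: conversion happens before entry, and the drug and dose needed to repeat it are not stored.

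**Conclusion.** The point holds as a contradiction between section 7.2.5 and Appendices 1 and 2, with a real but bounded consequence for one secondary endpoint in the subset of subjects taking opioids. From the database alone, MME/day cannot be recomputed, and subjects who switched opioid cannot be identified.

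For an affected subject with unchanged intake, the apparent fall is 20% to 50% if the factor drops by a ratio of 1.25 to 2.0. The effect on the mean is much smaller: 2% to 5% of baseline if 10% of users are affected in one direction, and less if errors run both ways. The ratios and the share are assumptions, because the protocol gives neither. The mismatch and the loss of information do not depend on them. The change should be made, because it is cheap now and the missing data may not be recoverable later.

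**What to change.** In Appendices 1 and 2, replace the single MME field with repeatable rows for opioid name, route and total daily mg, for existing and for newly started opioids. The baseline form already uses repeatable name-and-dose rows for the five other classes, so only the route field is new in kind. Derive MME centrally with one conversion table, named with its version in the protocol or the statistical analysis plan, and keep the entered drug and dose so that the derivation can be repeated. Separate rows would also settle whether the MME asked for a new opioid is meant to include the existing one, which Appendix 2 leaves open.

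The cost is a few form fields, one lookup table and slightly more entry for opioid users. If the sponsor keeps the single field, section 7.2.5 should drop opioid type, and the protocol should state that MME is site-converted and cannot be recomputed.
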